4.1 Medication Selection at discharge

Inclusion Criteria: All patients.

We will use logistic regression with GEE to account for within hospital clustering to evaluate whether copayment intervention is associated with discharge P2Y₁₂ inhibitor type. We will use the same methods for adjustment as in the primary analysis.

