ARTEMIS is a prospective cluster-randomized clinical trial that will evaluate whether patient copayment reduction significantly influences antiplatelet selection and long-term adherence. This study will also examine patient outcomes and the overall cost of care after AMI. After IRB approval, sites will be randomized to either the intervention or the control. Randomization will be stratified by annual site AMI volume and proportion of ticagrelor use using medians across potential sites as cut-offs for identifying high vs. low categories. Approximately 11,000 patients with STEMI or NSTEMI will be enrolled at approximately 300 hospitals.

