1.2 Secondary Objectives

To evaluate whether reducing patient copayments affects selection of P2Y₁₂ receptor inhibitor medication at discharge.

To assess the impact of copayment reduction on the total cost of health care for patients after AMI.

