6.1 Non-persistence with antiplatelet therapy at 1 year

Propensity matched analysis: Within each of the four randomization strata defined, using medians across potential sites from survey conducted prior to ARTEMIS, by high (≥ 400) vs. low (< 400) annual site AMI volume and high ($\geq 15\%$) vs. low ($< 15\%$) proportion of ticagrelor use and by randomization scheme (2:1 vs. 1:1), we will match intervention arm patients to usual care patients. Matching within randomization scheme and strata forces matches across sites of similar size and proportion ticagrelor use and time of site randomization. To run the computerized

Statistical Analysis Plan

matching of intervention to usual care patients, we will utilize the gmatch macro publicly available from the Mayo Clinic Division of Biomedical Statistics and Informatics website of locally written SAS macros. This macro was downloaded on 5/13/13 from the following website: <http://mayoresearch.mayo.edu/mayo/research/biostat/sasmacros.cfm>. The gmatch macro performs greedy matching of cases to controls (intervention patients to usual care patients) within a pre-specified caliper. Greedy matching starts by creating two pools of patients; 1 pool for intervention patients and 1 pool for usual care. Each pool is randomly sorted, then for each intervention patient, we select the first usual care patient in the randomly sorted pool that has a propensity score within the pre-specified caliper. Once a match is made, it is never broken even if another closer match exists. Patients will be matched based on the propensity for intervention group using the propensity score estimated in the primary analysis. If there are no usual care patients with a propensity score within the caliper of a given intervention patient then that intervention patient is not included in the matched sample. We will match on the logit of the propensity score and use a caliper with a width of 0.2 times the standard deviation of the logit of the propensity score as suggested by Austin [7]. To estimate the intervention effect on non-persistence among the propensity matched sample we will fit a logistic regression model stratified by matched pair. Matching on the propensity score is expected to reduce most of the observed differences in patient case mix between the two groups so further adjustment is not necessary.

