8.2 Appendix: Table Shells

8.2.1 Main Table Shells

Table 1: Site Characteristics by Copayment Intervention

	Overall (N=)	Copayment Intervention (N=)	Usual Care (N=)
N patients enrolled			
MI volume			
% high (≥ 400) MI volume			
Site % baseline ticagrelor use			
% high ($\geq 15\%$) baseline ticagrelor use			
Region			
Randomization scheme			
Total bed size			
Teaching status			
Government hospital			
Member of a healthcare network			
Surgery capabilities			

Statistical Analysis Plan

Table 2a: Patient Level Baseline Characteristics by Copayment Intervention

	Overall (N=patients)	Copayment Intervention (N=patients)	Usual Care (N=patients)
Age			
Gender, % male			
Non-white race			
Hispanic ethnicity			
Private insurance			
Prior MI			
Prior PCI			
Prior CABG			
Prior stroke/TIA			
Prior heart failure			
Dialysis			
PAD			
Hypertension			
Diabetes			
Current/recent smoker			
Weight			
Transfer in			
STEMI			
Home P2Y12 inhibitor			
Home aspirin			
Creatinine Clearance			
Nadir hemoglobin			
Multivessel disease			
Access Site			
PCI performed			
CABG performed			
Drug-eluting stent			
In-hospital or prior bleeding			
In-hospital MI			
In-hospital stroke			
Cardiogenic shock (Killip IV on presentation or in- hospital cardiogenic shock)			

Statistical Analysis Plan

Heart failure (Killip II/III on presentation or in-hospital heart failure)			
Cardiac Arrest			
Health Literacy			
Baseline angina frequency			
Cardiac Rehab			
Baseline PHQ2>3			
Baseline EQ5D VAS			
Married			
Employed			
Education (college graduate)			
Baseline financial hardship			
Missed >1 dose of medication in the last month			

Statistical Analysis Plan

Table 2b: Cluster Level Summary Data of Baseline Characteristics by Copayment Intervention

	Overall (N=sites)	Copayment Intervention (N=sites)	Usual Care (N=sites)
Randomization Scheme			
Site MI volume			
Site % Ticagrelor			
Age			
Gender, % male			
Non-white race			
Hispanic ethnicity			
Private insurance			
Prior MI			
Prior PCI			
Prior CABG			
Prior stroke/TIA			
Prior Heart Failure			
Dialysis			
PAD			
Hypertension			
Diabetes			
Current/recent smoker			
Weight			
Transfer in			
STEMI			
Home P2Y ₁₂ inhibitor			
Home aspirin			
Creatinine Clearance			
Nadir hemoglobin			
Multivessel disease			
Access Site			
PCI performed			
CABG performed			
Bare Metal Stent			
In-hospital or prior bleeding			
In-hospital MI			
In-hospital stroke			

Statistical Analysis Plan

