8.3 Appendix: List of Adjustment Variables

8.3.1 Adjustment Variables for Primary Models

Variable	Variable Type
Intervention	Yes/no
Randomization scheme	Categorical (2:1 vs. 1:1 scheme)
Interaction* between intervention and randomization scheme	Categorical
Site MI volume	Categorical (high vs. low)
Site % Ticagrelor use	Categorical (high vs. low)
Age	Continuous
Male gender	Yes/no
Race	Categorical (white vs. nonwhite)
Insurance Payors	Categorical (private vs. non-private)
Region	Categorical (Northeast, West, South, vs. Midwest)
Propensity for intervention	Continuous

*We will test for significant interaction and will drop if the interaction term is not significant.

Statistical Analysis Plan

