8.3.2 Variables for Propensity Score Model

[figure not shown]
Variable	Variable Type
Randomization scheme	Categorical (2:1 vs. 1:1 scheme)
Age	Continuous
Age >=65 vs. <65	Yes/no
Male gender	Yes/no
Race	Categorical (white vs. nonwhite)
Ethnicity	Categorical (Hispanic vs. non-Hispanic)
Insurance Payors	Categorical (private vs. non-private)
Prior MI	Yes/no
Prior PCI	Yes/no
Prior CABG	Yes/no
Prior stroke/TIA	Yes/no
Prior Heart failure	Yes/no
Dialysis	Yes/no
PAD	Yes/no
Hypertension	Yes/no
Diabetes	Yes/no
Current/recent smoker	Yes/no
Weight	Continuous
Transfer in	Yes/no
STEMI	Yes/no
Home P2Y ₁₂ inhibitor	Yes/no
Home aspirin	Yes/no
Creatinine Clearance	Continuous
Nadir hemoglobin	Continuous
Multivessel disease	Yes/no
Access Site	Categorical (Femoral vs. other)
PCI performed	Categorical (multivessel vs. culprit vs. none)
CABG performed	Yes/no
Drug-eluting stent implanted	Yes/no
In-hospital or prior bleeding	Yes/no
In-hospital MI	Yes/no
In-hospital stroke	Yes/no
Cardiogenic shock (Killip IV on presentation or in-hospital cardiogenic shock)	Yes/no
Heart failure (Killip II/III on presentation or in-hospital heart failure)	Yes/no
Cardiac Arrest	Yes/no
Cardiac Rehab Referral	Yes/no
Health Literacy	Yes/no (score >=10 vs. <10)
Baseline angina frequency	Categorical (100 vs. 70-90 vs. 0-60 points)
Baseline PHQ2>3	Categorical
Baseline EQ5D VAS	Continuous

Statistical Analysis Plan

Married	Yes/no
Employed	Yes/no
Education (college graduate)	Yes/no
Baseline financial hardship	Categorical (1 vs. 2/3 vs. 4/5)
Missed >1 dose of medication in the last month	Yes/no
Site: Total bed size	Continuous
Site: Teaching Status	Yes/no
Site: Government hospital	Yes/no
Site: Member of a Healthcare Network	Yes/no
Site: Surgery Capabilities	Yes/no

[figure not shown]

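### The drug-selection analysis in SAP 4.1 uses each hospital's pre-trial ticagrelor share only as high or low although the percentage is held, which gives up precision without causing bias

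*SAP*

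**What the plan says.** SAP 1.2 lists the objective: "To evaluate whether reducing patient copayments affects selection of P2Y₁₂ receptor inhibitor medication at discharge". Section 4.1 gives the model: "We will use logistic regression with GEE to account for within hospital clustering to evaluate whether copayment intervention is associated with discharge P2Y₁₂ inhibitor type". It then takes over the covariates of the primary models: "We will use the same methods for adjustment as in the primary analysis".

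Those covariates are listed in 8.3.1, where "Site % Ticagrelor use" is a two-level variable, high versus low. Section 6.1 gives the cut as 15% and its origin: "using medians across potential sites from survey conducted prior to ARTEMIS". The same two-level factor was used in the design: "Randomization will be stratified by annual site AMI volume and proportion of ticagrelor use using medians across potential sites as cut-offs".

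The propensity score in 8.3.2 contains five hospital variables: bed size ("Site: Total bed size", continuous), teaching status, government ownership, network membership and surgery capability. Ticagrelor share is not among them in any form.

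The percentage itself is held. The Table 1 shell has a row "Site % baseline ticagrelor use" separate from its row for the share of high-use sites, and Table 2b lists the site percentage again at cluster level.

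**The concern.** For persistence and MACE, a high/low ticagrelor term is an ordinary stratification covariate. For drug selection it is more than that: a hospital's ticagrelor share before the trial is the cluster-level baseline of the outcome. Section 4.1 inherits a covariate list built for other endpoints and so uses this baseline only as a median split. Hospitals at 16% and 30% are treated alike, as are hospitals at 0% and 14%.

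Two things follow. Variation between hospitals that the percentage could explain stays in the error term, and in a cluster trial that variation is a main part of the error. Chance differences between arms in pre-trial prescribing within the high and low strata also go unadjusted. The objective matters beyond its own result, because SAP 1.4 and 4.13 name use of a more potent agent as one of the routes by which MACE might fall.

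**Working it through.** **No figure to reproduce.** The SAP gives no power, effect size or ICC for drug selection. The design inputs reused below do reproduce for the persistence endpoint: design effect = 1 + ((0.65² + 1) × 36.67 − 1) × 0.025 = 2.28, and 11,000 / 2.279 = 4,827, as SAP 1.4 states.

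**Inputs from the SAP.** 300 sites, mean 36.67 patients per site, CV of cluster size 0.65, median cut at 15%, randomization stratified on the split, allocation 1:1 and later 2:1.

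**Assumptions, not in the SAP.** The outcome is ticagrelor versus any other agent. The standard deviation between sites on the logit scale is 0.6 to 1.0. The correlation ρ between the survey share and in-trial site use is 0.2 to 0.9.

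**Analytic step.** A median split of a normal covariate keeps 2/π = 0.64 of the variance that the full value would explain, so about 36% of it is lost. The residual between-site variance under the split, relative to that under the full value, is (1 − 0.64ρ²) / (1 − ρ²). At ρ = 0.5 this is (1 − 0.159) / 0.75 = 1.12. At ρ = 0.7 it is (1 − 0.312) / 0.51 = 1.35. These ratios overstate the effect on the estimate, because neither covariate form reduces patient-level variation within sites.

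**Simulation.** 2,000 trials per setting; weighted linear model of site proportions on arm plus the high/low term, or on arm plus the percentage. Ranges cover both allocation ratios and both between-site standard deviations.

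| ρ | Analytic between-site ratio | Simulated variance ratio, high/low vs percentage | Standard-error ratio |
|---|---|---|---|
| 0.3 | 1.04 | 1.01-1.02 | 1.01 |
| 0.5 | 1.12 | 1.06-1.11 | 1.03-1.05 |
| 0.7 | 1.35 | 1.16-1.23 | 1.08-1.11 |
| 0.9 | 2.55 | 1.42-1.79 | 1.19-1.34 |

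As an example, with 1:1 allocation and a between-site SD of 1.0, the standard error of the difference between arms falls from 2.06 to 1.96 percentage points at ρ = 0.5, and from 1.86 to 1.68 at ρ = 0.7. The percentage together with the high/low indicator does as well as the percentage alone, so keeping the stratification factor costs nothing.

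Further runs of the same kind gave an excess variance of 0-3% at ρ = 0.2-0.3, 15-22% at 0.7 and 29-42% at 0.85. The top of the range varies most with the model and weights.

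**Chance imbalance.** After stratification, the patient-weighted difference between arms in pre-trial share still has a standard deviation of about 0.9 points (between-site SD 0.6) to 1.5-1.6 points (SD 1.0). Its correlation with the estimate adjusted for high/low is about 0.1 at ρ = 0.3 and 0.4-0.5 at ρ = 0.9.

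**The case against.** The strongest reply is that nothing here is wrong or inconsistent. Sites were randomized within high/low strata, and the SAP adjusts for that factor in the form in which it was used, which is conventional and valid. That stands.

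A reader might infer that differences in pre-trial prescribing bias the result. The SAP does not support this. Allocation was random within strata, so differences that remain are chance. The GEE analysis clustered by hospital carries them into the confidence interval, and type I error is not affected.

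A reader might also take a large loss as established. It is not. The SAP does not say how accurate the survey was or how strongly it predicts in-trial prescribing, and at a correlation of 0.2-0.3 the gain is close to nil. The simulated models are also simpler than the planned one. Region, MI volume, insurance and the hospital variables in the propensity score may already explain some between-site variation. The ratios refer to a difference in proportions. In a logistic model, adding a prognostic covariate also shifts the odds ratio being estimated, so the gain need not show fully in the standard error of the log odds ratio.

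Finally, one might extend the point to MI volume or to the co-primary models, which share 8.3.1. There is no basis for that: MI volume is not a baseline value of drug choice, and no gain has been shown for persistence or MACE.

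What remains is narrow. A baseline measure of this outcome is in hand and is used in a coarser form than necessary.

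**Conclusion.** The point holds as a matter of efficiency for one secondary objective. The analysis in 4.1 is valid and unbiased under randomization, but it discards part of the information in a baseline measure that the sponsor already holds, and it leaves chance imbalance within strata unadjusted. The excess variance is about 0-3% at a correlation of 0.2-0.3, 6-11% at 0.5, 15-23% at 0.7 and roughly 30-40% at 0.85. These figures rest on assumed correlations and between-site spread and on simplified site-level models, and the other planned covariates may reduce them. The gain may be negligible or material; the SAP does not allow one to say which. The change is worth making because it costs almost nothing and should be fixed in advance: the same term added after results are seen would look data-driven.

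**What to change.** In 4.1, add one sentence stating that the drug-selection model also includes the recorded pre-trial ticagrelor percentage of each site, on the logit scale or as a simple spline, beside the high/low stratification indicator, which stays. State in advance how sites recorded at 0% are handled if the logit is used, since it is undefined there. Leave MI volume as it is, and make no change to the co-primary models.

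The cost is SAP wording and one or two degrees of freedom among about 300 sites. No new data are needed, because the values are already required for Tables 1 and 2b.

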4.2 Non-persistence with antiplatelet therapy at 1 year

Non-persistence or death vs. persistence at 1 year

Analogous to Section 3.1, we will examine the outcome of death or non-persistence; non-persistence still defined as interruption ≥ 30 days of P2Y₁₂ receptor inhibitor. The primary analysis will be a logistic regression model with generalized estimating equations (GEE) to account for within hospital clustering and adjustment for selected patient characteristics (Section 8.3.1) and a propensity score for intervention (Section 8.3.2). We will use the same propensity score described in section 3.1. Cluster heterogeneity will be quantified using ICCs calculated from unadjusted and adjusted models. We will calculate the ICCs across all hospitals and also by treatment group.

Non-persistence to initial P2Y₁₂ receptor inhibitor at 1 year

Analogous to Section 3.1, we will use the LOCF method for patients who died before one year or had missing 1 year P2Y₁₂ inhibitor status. Patients who have continued their initial P2Y₁₂ receptor inhibitor use at one year from discharge with less than 30 continuous days of interruption will be considered persistent. Patients who switched from their initial P2Y₁₂ receptor inhibitor will be considered non-persistent.

The primary analysis will be a logistic regression model with generalized estimating equations (GEE) to account for within hospital clustering and adjustment for selected patient characteristics (Section 8.3.1) and a propensity score for intervention (Section 8.3.2). We will use the same propensity score described in section 3.1. Cluster heterogeneity will be quantified using ICCs calculated from unadjusted and adjusted models. We will calculate the ICCs across all hospitals and also by treatment group.

4.3 Medication fill using pharmacy data only

Inclusion Criteria: Patients with pharmacy data collected.

Persistence:

Using pharmacy data, we will calculate persistence using the same definition as in the primary analysis with non-persistence defined as a fill gap ≥ 30 days. Analogous to Section 3.1, we will use the LOCF method for patients who died before one year or had missing 1 year P2Y₁₂ status. Persistence at 1 year will be compared by copayment intervention using logistic regression with GEE to account for within hospital clustering and the same methods for adjustment as in the primary analysis.

Adherence:

Using pharmacy data, we will calculate the proportion of days covered. Patients with proportion of days covered $\geq 80\%$ of expected prescriptions over one year of follow-up or until death date will be considered adherent. Adherence at 1 year will be compared by copayment intervention using logistic regression with GEE to account for within hospital clustering and the same methods for adjustment as in the primary analysis.

4.4 Medication Drug Levels

Inclusion Criteria: All patients with valid drug level data.

A subset of patients will have blood drawn over the one year of follow-up after AMI. This blood draw will be randomly assigned to 250 patients (125 in each arm) at each of the following follow-up time points: 3, 6, 9, or 12 months. Drug levels or metabolites of clopidogrel or ticagrelor will be measured, as appropriate. Persistence (yes vs. no) will be defined based on clinically selected cut-offs of minimum drug levels. Medication drug level data will be presented in Table 6 in Section 8.2.1.

4.5 Comparison of Medication Use from different sources

Overall and stratified by copayment reduction, we will assess agreement among patient reported medication use, medication fill adherence, and drug levels using Kappa statistics and summarize using frequencies and percentages (Table 7 in Section 8.2.1).

4.6 Cost

A detailed description of the healthcare resource utilization endpoints and analysis will be contained in a separate SAP, drafted following and guided by the primary clinical endpoint results.

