Patient-reported persistence to antiplatelet therapy will be validated using pharmacy records that will be collected on a subset of the overall study population. The assumed standard deviation of 0.25 (for the proportion of days covered) is based on a recent randomized clinical trial to assess an intervention designed to improve adherence [4]. Assuming 1:1 randomization and a two-sided Type I error rate of 0.05, a sample size calculation based on the two-sample t-test suggests that a total sample size of 1644 patients will yield 90% and a total sample size of 2034 will yield 95% power. A random sample of 2400 patients from the 300 sites randomized with a CV of 0.25 and an ICC of 0.025 would yield a design effect of approximately 1.26. The resulting effective sample size of 2021 patients would yield approximately 95% power to detect a difference of 4% between the patient copayment reduction intervention and control groups. The target sample size of 2500 patients with pharmacy records allows for 4% missing data due to records that are not available.

2. General Considerations for Data Analysis

We will include a detailed flow diagram showing the number of participants' eligible, number of subjects randomized to Copayment Intervention and Usual Care arms, numbers of subjects lost to follow-up or excluded from analyses, and the number of subjects analyzed for the key study endpoints. Additionally, we will describe the number of clinical sites in Copayment Intervention and Usual Care arms including the mean (median, range) for key study elements by site. Key elements will include the following items: descriptions of participants, interventions, objectives, outcomes, and sample size justification; and details about the randomization procedure, factors used to stratify randomization, (lack of) blinding, statistical methods, participant flow, dates of recruitment, baseline data by individuals and by cluster, numbers analyzed, outcomes and estimation, adverse events, and a discussion. These elements are based on the CONSORT statement for cluster randomized studies [5].

After Steering Committee consensus, the randomization scheme was changed from 1:1 to 2:1 Usual Care vs. Intervention effective November 16, 2015. Randomization schema was added below as a covariate for adjustment.

All analyses will be conducted using SAS version 9.4 or higher software. All tests will be two-sided and a p-value of <0.05 will be considered statistically significant.

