3.2 MACE

The primary study objective evaluates whether patient copayment reduction leads to lower risk of MACE at one year. MACE is defined as the composite of all-cause death, recurrent myocardial infarction, and stroke. Follow-up will be censored at time of study withdrawal or last known alive. The time-to-first MACE event up to one year post-discharge will be compared between intervention and control arms. Cumulative incidence rates will be presented as Kaplan-Meier curves and in tables for 30 days, 6 months, and 1 year post-discharge. The primary analysis will be a Cox proportional hazards model accounting for within hospital clustering using robust standard errors and adjustment for selected patient characteristics (Section 8.3.1) which includes a propensity score for intervention. We will use the same propensity score described in section 3.1. Cluster heterogeneity will be quantified using ICCs calculated from unadjusted and adjusted models. We will calculate the ICCs across all hospitals and also by treatment group.

After Steering Committee consensus, the randomization scheme was changed from 1:1 to 2:1 Usual Care vs. Intervention effective November 16, 2015. Randomization schema was added as a covariate for adjustment as shown in Section 8.3.1 and to the propensity model as shown in Section 8.3.2.

4. Secondary Endpoints

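### The SAP for total cost, a secondary objective, is to be written after the primary clinical results and guided by them, so the cost comparison is not fully pre-specified

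*SAP*

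**What the plan says.** The introduction to the SAP announces cost as part of the study: "This study will also examine patient outcomes and the overall cost of care after AMI". Section 1.2 then lists it as the second of two secondary objectives: "To assess the impact of copayment reduction on the total cost of health care for patients after AMI".

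Section 4.6, under Secondary Endpoints, is one sentence. It says first where the content will be found: "A detailed description of the healthcare resource utilization endpoints and analysis will be contained in a separate SAP". It then says that this separate SAP will be "drafted following and guided by the primary clinical endpoint results". The deferral covers both the endpoints and the analysis.

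Section 2 applies one significance rule without exception: "All tests will be two-sided and a p-value of <0.05 will be considered statistically significant". The list of outputs (Section 8.1) and the table shells (Section 8.2) contain no cost table.

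**The concern.** Pre-specification means that the endpoint and the method are fixed by people who do not yet know how the arms compare. Section 4.6 sets the opposite order for cost: the clinical comparison is made first, and the cost endpoints and methods are then written in its light.

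The choices left open by this SAP can each move a cost comparison: which components are counted, whose perspective is taken, over what period, whether the cost of the voucher itself is included, how skewed, censored or missing costs are handled, and how clustering enters the model. If they are made with the arm-level clinical results in view, a reader of the eventual cost result cannot tell whether they were made on their merits. At stake is the standing of one of the two secondary objectives. The co-primary conclusions are not at stake.

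**Working it through.** There is no stated figure to reproduce. The SAP gives no sample size, power, effect size or variance for cost. The check sets its statements side by side.

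1. **Status of cost.** Section 1.2 makes it a secondary objective and Section 4.6 sits among the secondary endpoints. The SAP has a separate heading for exploratory work (Section 4.13), and cost is not placed there. The general 0.05 rule in Section 2 has no exception for it. As written, cost is a secondary comparison with an ordinary test.

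2. **What is fixed in this SAP.** Only the broad quantity, total cost of health care after AMI. No cost endpoint definition, perspective, time horizon, model or rule for missing or censored costs appears in Section 4.6, the output list or the table shells.

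3. **When and on what basis the rest is fixed.** After the primary clinical results and guided by them. This is an explicit rule, so the point does not depend on a missing detail.

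4. **What those results are.** They are the co-primary endpoints: non-persistence (Section 3.1) and MACE (Section 3.2). On the second, the SAP says: "MACE is defined as the composite of all-cause death, recurrent myocardial infarction, and stroke". Recurrent infarction and stroke plausibly generate hospital and other care. Persistence bears directly on drug spending.

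5. **Do they reveal the cost result?** They are informative but not decisive. Take the effects assumed in Section 1.4:
   - Persistence rises from 70% by 4 percentage points, so 4 more persistent patients per 100.
   - MACE falls from 12.0% to 9.84%: 12.0 − 9.84 = 2.16 points, so about 2 fewer patients with an event per 100.

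   The first effect raises drug cost, more so if use shifts to the brand agent that the voucher covers (Section 2.2). The second would be expected to lower the cost of care for events. With no unit costs in the document, the sign of the net difference stays open even if both hypotheses succeed.

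6. **Is there a safeguard?** Section 2 includes among the items to be reported "factors used to stratify randomization, (lack of) blinding, statistical methods", so arm assignment is not concealed by design. Nothing in this SAP separates the authors of the cost SAP from the arm-level results, and Section 4.6 intends that they use them.

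Steps 1 to 4 and 6 establish the point. Step 5 limits it.

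**The case against.** The strongest reply is that the known results will be clinical, not economic. Section 4.6 does not say that cost will have been compared by arm, or even looked at, when the cost SAP is written. A plan completed before the cost comparison is still written ahead of its own outcome. This is right as far as it goes, and it rules out the stronger inference that cost methods would be picked to fit a cost result already seen. It does not restore full pre-specification, because the clinical results carry information about cost.

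Second, a reader might infer that the primary results largely give away the direction of the cost difference. The documents do not support that: the two hypothesised effects pull cost in opposite directions, and no unit costs are given.

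Third, a reader might attach a false-positive figure, for example 1 − (1 − 0.05)³ = 0.143 for the best of three independent 5% tests. That calculation supposes that someone sees three cost p-values and keeps one. Section 4.6 describes no such step, and alternative cost measures on the same patients would not be independent. The figure should not be used.

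Fourth, the protocol is not at hand and may fix the perspective, horizon or cost measure; Section 2.3 refers to it for an analysis choice. So these cannot be called unfixed in the trial as a whole. Even so, the sentence in Section 4.6 places the detailed endpoints and analysis after the results.

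Fifth, some economic work sensibly depends on the clinical outcome, such as whether a cost-effectiveness analysis is worth running. That is accepted. It can be met by a conditional rule written beforehand and does not require leaving the basic between-arm comparison of total cost open.

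**Conclusion.** The point holds, limited to the clause on timing and guidance. As written, Section 4.6 permits the main cost endpoint and model to be chosen with knowledge of arm-level results that are informative about cost, so the comparison serving this secondary objective could not be called fully pre-specified.

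The size cannot be stated as a number from this document. The conclusion rests on two assumptions: that MACE and persistence bear on health-care cost, which is plausible but not quantified in the SAP, and that no document outside this one already fixes the main cost comparison. It shows an opportunity for result-guided choice, not that such a choice was made. The planned analyses of the co-primary endpoints do not depend on it. The change is worth making because it affects the credibility of a stated objective and requires only that a document already planned be written earlier.

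**What to change.** Replace the sentence in Section 4.6 with text to this effect:

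- The main between-arm cost comparison will be finalised and dated before arm-level primary results are available. It will fix the primary cost measure, perspective, time horizon, handling of voucher cost, handling of censored or missing costs, and a model that accounts for clustering by hospital.
- Any economic analysis that truly depends on the clinical result, such as whether to run a cost-effectiveness analysis, will be set out in the same document as a conditional rule.
- Anything specified after the clinical results are known will be labelled post hoc or exploratory.

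If the arm-level results are already known when the change is considered, the first step is no longer open and the label in the third should apply to the cost analysis. If the protocol already fixes some of these items, a cross-reference is enough for them.

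The cost is earlier drafting and somewhat less freedom to tailor the economic analysis. No new data or patients are needed, and the co-primary analyses do not change.
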